4.2.3 Rationale for the Selected Participant Population

Household contacts living with a SARS-CoV-2-infected individual will comprise the participant population in this study. As noted in Section 2.1, household contacts are at elevated risk of developing COVID-19 due to their extended close proximity with this individual who is shedding virus and therefore, are potential candidates for prophylaxis with MOV.

In this study, a household is defined as a unit with shared living space(s) with no more than 10 inhabitants (ie, large communal living arrangements such as dormitories, hostels, barracks, and long-term care facilities do not qualify as households). There is no requirement that the household residents share a familial relationship.

The primary endpoint is analyzed in those without detectable SARS-CoV-2 virus at baseline (ie, the Day 1 NP swab; those with detectable virus prior to randomization are ineligible). Recent data from a study of household prophylaxis with casirivimab and imdevimab [O'Brien, M. P., et al 2021] showed that COVID-19 incidence rates are substantially higher in the population that has detectable virus via PCR at baseline than in the population that does not have detectable virus at baseline. The viral status is not known at the time of randomization due to the duration required for RT-PCR testing. Since randomization cannot therefore be stratified to assure balance between the arms, the 2 populations will be analyzed both separately and together for onset of disease. It is assumed that up to 20% of the enrolled population may have detectable virus at baseline, in consideration of the virus-positive (or viral status unknown) percentage (16.5%) reported by O'Brien [O'Brien, M. P., et al 2021] and a conservative adjustment to 20% based on the higher infectivity of more recently reported viral variants.

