9.4.1 Efficacy Endpoints

The primary efficacy endpoint is the percentage of participants with undetectable SARS-CoV-2 in baseline NP swabs developing COVID-19 (laboratory-confirmed SARS-CoV-2 infection with symptoms) through Day 14.

The secondary efficacy endpoints are:

- Percentage of participants (regardless of SARS-CoV-2 results in baseline NP swabs) developing COVID-19 through Day 14
- Percentage of participants with undetectable SARS-CoV-2 in baseline NP swabs developing COVID-19 through Day 29
- Percentage of participants with undetectable SARS-CoV-2 in baseline NP swabs having viral transmission through Day 14

• Percentage of participants with detectable SARS-CoV-2 in baseline NP swabs developing COVID-19 through Day 14

The exploratory efficacy endpoints are:

- Percentage of participants (regardless of SARS-CoV-2 results in baseline NP swabs) developing COVID-19 through Day 29
- Percentage of participants with detectable SARS-CoV-2 in baseline NP swabs developing COVID-19 through Day 29
- Percentage of participants with undetectable SARS-CoV-2 in baseline NP swabs having viral transmission through Day 29
- Percentage of baseline seronegative participants with undetectable SARS-CoV-2 in baseline NP swabs developing anti-SARS-CoV-2 antibodies through Day 29
- Severity of laboratory-confirmed COVID-19 through Day 29 using NIAID ordinal scale criteria
- Participant-reported symptoms severity (for specified COVID-19 symptoms) in participants who develop laboratory-confirmed COVID-19 on or before Day 14
- Change from baseline in SARS-CoV-2 RNA titer and percentage of participants with undetectable SARS-CoV-2 RNA in NP swabs at Day 14 in participants with detectable SARS-CoV-2 in NP swabs at baseline
- Viral RNA mutation rate and detection of treatment-emergent sequence variants as assessed by comparison of viral gene sequencing at baseline and postbaseline in participants who develop laboratory-confirmed COVID-19 on or before Day 14
- Percentage of participants who develop laboratory-confirmed COVID-19 on or before Day 14 utilizing health care related to COVID-19 through Day 29
- Generic health-related quality-of-life in participants through Day 29 via EuroQoL Five Dimension Questionnaire (EQ-5D-5L)

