9.5 Analysis Populations

9.5.1 Efficacy Analysis Populations

The mITT will serve as the primary population for the analysis of efficacy data in this study. The mITT consists of all randomized participants who received at least 1 dose of study intervention. The primary objective will be assessed in the mITT-VN population, which consists of the subset of the participants in the mITT with undetectable SARS-CoV-2 in baseline NP swabs (ie, virus negative/undetectable at baseline). The mITT-VP population, consisting of the subset of the participants in the mITT with detectable SARS-CoV-2 in baseline NP swabs (ie, virus-positive/detectable at baseline) will be used in some of the exploratory analyses. Under certain extenuating circumstances (Section 8.2.5), eg, when only qualitative OP swab results are available from the central laboratory, qualitative OP swab results can be used to derive the baseline viral status.

A supportive analysis using the Per-Protocol population will be performed for the primary efficacy endpoint. The Per-Protocol population excludes participants from the mITT due to deviations from the protocol that may substantially affect the results of the primary efficacy endpoints. Participants with prophylaxis outcomes of "indeterminate" (Section 8.2.6) will be excluded from the Per-Protocol population. Moreover, participants who took <80% of the required doses will be excluded from the Per-Protocol population.

The final determination on protocol deviations, and thereby the composition of the Per-Protocol population, will be made prior to the final unblinding of the database and will be documented in a separate memo.

Due to the conflict in Ukraine, participants in Ukraine who were randomized in FEB-2022 with incomplete data for the primary endpoint (ie, no clinical outcome assessment on Day 14) will be excluded from the efficacy analyses in the mITT population.

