For the evaluation of the prevention of viral transmission using MOV compared with placebo through Day 14 among participants with undetectable SARS-CoV-2 in NP swabs at baseline, the percentage of participants in the 2 intervention groups who have positive/detectable SARS-CoV-2 RNA through Day 14 will also be compared using the stratified Miettinen and Nurminen method [Miettinen, O. and Nurminen, M. 1985] (stratified by age and household size as described in Section 6.3.2).

The efficacy of MOV compared with placebo for the prevention of COVID-19 with respect to the percentage of participants with detectable SARS-CoV-2 in baseline NP swabs developing COVID-19 through Day 14 will be evaluated. The difference in percentages between treatment groups (MOV minus placebo) and the associated 95% CI will be calculated using the Miettinen and Nurminen method with CMH weights [Miettinen, O. and Nurminen, M. 1985].

A detailed analysis strategy for key efficacy endpoints is listed in Table 5.

Endpoint/Variable (Description, Time Point)	Primary vs Supportive Approach ^a	Statistical Method	Analysis Population	Missing Data Approach
Primary				
Percentage of participants with undetectable SARS-CoV-2 in baseline NP swabs developing COVID-19 by Day 14	Р	Stratified M&N method with CMH weights ^b	mITT-VN	As described in 9.6.1
Percentage of participants with undetectable SARS-CoV-2 in baseline NP swabs developing COVID-19 by Day 14	S	Stratified M&N method with CMH weights ^b	РР	Observed data only
Secondary				
Percentage of participants (regardless of SARS-CoV-2 results in baseline NP swabs) developing COVID-19 by Day 14	Р	Stratified M&N method with CMH weights ^b	mITT	As described in 9.6.1
Percentage of participants (regardless of SARS-CoV-2 results in baseline NP swabs) developing COVID-19 by Day 14	S	Stratified M&N method with CMH weights ^b	РР	Observed data only

Table 5	Analysis	Strategy	for Kev	Efficacy Endpoin	nts
1 4010 5	1 mary 515	Shategy	101 1109	Lineacy Linapon	110

Endpoint/Variable (Description, Time Point)	Primary vs Supportive Approach ^a	Statistical Method	Analysis Population	Missing Data Approach
Percentage of participants with undetectable SARS-CoV-2 in baseline NP swabs developing COVID-19 by Day 29	р	Stratified M&N method with CMH weights ^b	mITT-VN	As described in 9.6.1
Percentage of participants with undetectable SARS-CoV-2 in baseline NP swabs developing COVID-19 by Day 29	S	Stratified M&N method with CMH weights ^b	РР	Observed data only

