Percentage of participants who develop positive/detectable SARS-CoV-2 through Day 14 among those with undetectable SARS-CoV-2 in NP swabs at baseline	р	Stratified M&N method with CMH weights ^b	mITT-VN	M=C ^c
Percentage of participants who develop positive/detectable SARS-CoV-2 through Day 14 among those with undetectable SARS-CoV-2 in NP swabs at baseline	S	Stratified M&N method with CMH weights ^b	РР	Observed data only
Percentage of participants with detectable SARS-CoV-2 in baseline NP swabs developing COVID-19 by Day 14	р	Stratified M&N method with CMH weights ^b	mITT-VN	As described in 9.6.1
Percentage of participants with detectable SARS-CoV-2 in baseline NP swabs developing COVID-19 by Day 14	S	Stratified M&N method with CMH weights ^b	РР	Observed data only

C=case of COVID-19; CMH=Cochran-Mantel-Haenszel; M=missing; M&N=Miettinen and Nurminen; mITT-VN=modified intent-to-treat population with undetectable SARS-CoV-2 in baseline NP swabs; NP=nasopharyngeal; PP=per-protocol.

^a P=Primary approach; S=Supportive approach.

^b Miettinen and Nurminen method with CMH weights stratified by age and household size.

^c M=C is Missing considered as a case of COVID-19.

Participants in Ukraine who were randomized in FEB 2022 without clinical outcome assessment on Day 14 will be excluded from the efficacy analysis.

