9.9.2 Sample Size and Power Calculations for Efficacy Analyses (Secondary Objective)

The secondary endpoint associated with a hypothesis of this study is the percentage of participants developing COVID-19 through Day 14, regardless of SARS-CoV-2 results in baseline NP swabs. The related analysis population will consist of participants in the mITT population (see Section 9.5.1), approximately 1376 participants.

The power and sample size calculation for the secondary objective were computed using EAST and based on the following assumptions in addition to the assumptions listed in the previous section:

- The percentage of participants with detectable SARS-CoV-2 in baseline NP swabs is assumed to be 20% among the 1376 participants (see Section 4.2.3), resulting in approximately 276 participants with detectable SARS-CoV-2 in baseline NP swabs.
- The background secondary attack rate, in the absence of MOV, for participants with detectable SARS-CoV-2 in baseline NP swabs, is assumed to be ~40% based on the secondary attack rate calculated for the virus-positive participants in the REGEN-COV[™] prophylaxis study [O'Brien, M. P., et al 2021] [Food and Drug Administration 2021].
- The secondary attack rate for participants in the MOV group with detectable SARS-CoV-2 in baseline NP swabs is ~28% (with a risk reduction of 30% relative to the placebo group based on the reduction observed with REGEN-COV[™] in this population)
 [O'Brien, M. P., et al 2021] [Food and Drug Administration 2021].

Since the SARS-CoV-2 viral status at baseline will not be available before randomization, there is a potential imbalance in the 2 study intervention groups for participants with undetectable and detectable SARS-CoV-2 in baseline NP swabs. This also leads to different potential allocation ratios of participants with undetectable versus detectable SARS-CoV-2 in baseline NP swabs in the 2 study intervention groups. Assessment of power for this comparison is presented under 3 selected scenarios in Table 8:

 Scenario with more participants with detectable SARS-CoV-2 in baseline NP swabs in the MOV group (as listed in Table 7). There are approximately 188 participants with detectable SARS-CoV-2 in baseline NP swabs and 500 participants with undetectable SARS-CoV-2 in baseline NP swabs randomized to the MOV group. Approximately 88

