9.10 Subgroup Analyses

To determine whether the treatment effect is consistent across various subgroups, the estimate of the between-group treatment effect (with a nominal 95% CI) for the primary endpoint will be estimated and plotted within each category of each subgroup. The following are examples of classification variables:

- Baseline SARS-CoV-2 NP swab result (undetectable, detectable)
- Baseline serology result for anti-SARS-CoV-2 antibodies (positive, negative)
- Age category (≤ 60 , > 60 years)
- Household size (≤ 3 , >3 household residents)
- Sex (female, male)
- Race (American Indian or Alaska Native, Asian, Black or African American, White)
- Geographic region (North America, Europe, Asia Pacific, Latin America, Africa)

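### Table 5 assigns the baseline-undetectable population (mITT-VN) to the Day 14 endpoint in baseline-detectable participants, so the primary-approach row selects nobody; mITT-VP appears to be intended

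*Combined protocol and SAP*

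**What the plan says.** Section 9.4.1 lists among the secondary efficacy endpoints "Percentage of participants with detectable SARS-CoV-2 in baseline NP swabs developing COVID-19 through Day 14". Section 3 gives the matching secondary objective, without a hypothesis. The Section 9.6.1 text says the treatment difference and its 95% CI will be calculated by the Miettinen and Nurminen method. That text describes the participants as detectable at baseline but names no analysis set. It then says: "A detailed analysis strategy for key efficacy endpoints is listed in Table 5".

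In Table 5 the primary-approach (P) row for "Percentage of participants with detectable SARS-CoV-2 in baseline NP swabs developing COVID-19 by Day 14" gives the analysis population as mITT-VN. The table footnote reads "mITT-VN=modified intent-to-treat population with undetectable SARS-CoV-2 in baseline NP swabs". Section 9.5.1 and Appendix 10 define mITT-VN in the same way.

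Section 9.5.1 also defines mITT-VP, the detectable subset of the mITT, and says it "will be used in some of the exploratory analyses". Appendix 10 defines it too. It appears nowhere in Table 5 or its footnotes. Section 4.2.3 says, of participants with and without detectable virus at baseline, that "the 2 populations will be analyzed both separately and together for onset of disease".

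**The concern.** The endpoint requires detectable virus at baseline, and the named population requires undetectable virus at baseline. Nobody can satisfy both, so the row as printed specifies an analysis of an empty set.

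Table 5 matters here because the Section 9.6.1 text hands the detail over to it. For this endpoint the table is the only place in the plan where an analysis population is named, and the name is wrong. A programmer working from the table gets no output. One who looks to Section 9.5.1 for a correction finds mITT-VP mentioned for exploratory analyses, whereas this endpoint is secondary.

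What is at stake is the prespecification of one secondary estimate. The confirmatory tests are not involved.

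**Working it through.** **Step 1: compare endpoint and population in every primary-approach row of Table 5.**

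| Endpoint | Baseline status the endpoint requires | Population named | Consistent? |
|---|---|---|---|
| COVID-19 by Day 14 (primary, H1) | Undetectable | mITT-VN | Yes |
| COVID-19 by Day 14 (secondary, H2) | Any | mITT | Yes |
| COVID-19 by Day 29 | Undetectable | mITT-VN | Yes |
| Detectable virus through Day 14 | Undetectable | mITT-VN | Yes |
| COVID-19 by Day 14 | Detectable | mITT-VN | No |

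The supportive rows all use PP. Section 9.5.1 builds PP from the mITT without restricting it by baseline swab, so the supportive row for this endpoint is not empty. The error is confined to one cell.

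**Step 2: look for the right population elsewhere in the plan.**

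- The Section 9.6.1 text describes the participants but names no set.
- Section 9.5.1 mentions mITT-VP for some exploratory analyses. It neither includes nor excludes this secondary use.
- Section 4.2.3 commits to separate analyses by baseline status but names no set.
- Section 9.10 lists baseline swab result as a subgroup variable, but for the primary endpoint, which is itself restricted to undetectable participants.

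So mITT-VP can be inferred, but it is not stated.

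**Step 3: size of the set the row should select.** Section 9.9.2 assumes 20% of 1376 are detectable at baseline:

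- 0.20 × 1376 = 275.2, and 1376 − 1100 = 276. Both agree with the plan's figure ("resulting in approximately 276 participants with detectable SARS-CoV-2 in baseline NP swabs").
- Equal-allocation scenario in Table 8: 138 per arm.
- Number falling in mITT-VN: 0.

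**Step 4: what the corrected row could deliver.** Section 9.9.2 assumes attack rates of about 40% on placebo and 28% on MOV in this group.

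- Expected cases: placebo 138 × 0.40 = 55.2; MOV 138 × 0.28 = 38.6.
- Difference (MOV minus placebo): 0.28 − 0.40 = −0.120.
- Unstratified Miettinen-Nurminen 95% CI: −0.229 to −0.008.
- Wald check: SE = √(0.24/138 + 0.2016/138) = 0.0566, and −0.120 ± 1.96 × 0.0566 gives −0.231 to −0.009.
- Whole counts, 39/138 against 55/138: difference −0.116, Miettinen-Nurminen 95% CI −0.225 to −0.004.

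These intervals illustrate the information in the analysis. They do not measure any bias caused by the label.

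**Step 5: effect on design figures.** With the planned detectable counts, a pooled two-proportion calculation (one-sided alpha 0.025) on the mixed event rates gives power of 24.0%, 95.6% and above 99% for the three Table 8 scenarios. The plan states 24, 95 and >99. None of these figures depends on the Table 5 label, so correcting it changes nothing in Section 9.9.

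**The case against.** The strongest reply is that this is an editorial slip with only one possible reading. Section 9.5.1 makes the mITT the primary efficacy population. The endpoint restricts itself to baseline-detectable participants wherever it is described: Section 3, Section 9.1, Section 9.4.1, the Section 9.6.1 text and the Table 5 row itself. The mITT restricted to detectable participants is mITT-VP by definition. The alternatives fail: mITT-VN is empty, the full mITT belongs to the H2 endpoint, and PP is assigned to the supportive row. The wrong label therefore leaves no data-dependent choice. The endpoint also has no hypothesis, and the interval in Step 4 describes a hypothetical result, not damage done by the error. It is also unstratified, whereas the row calls for the stratified method.

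Most of this stands. The intended population is clear by inference, the consequence is small, and the interval should carry no weight in judging how serious the error is. What does not follow is that the row can stay as it is. It is the operative specification of the primary approach to a listed secondary endpoint, and followed exactly it yields no estimate. The only sentence giving mITT-VP a use points to exploratory analyses. The mITT label also carries content beyond swab status, namely randomization and at least one dose taken, and that should be stated rather than deduced. A PDF extraction fault is an unlikely explanation: the neighbouring rows are intact and the footnote omits mITT-VP as well.

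**Conclusion.** The concern holds. One primary-approach row of Table 5 names a population containing 0 of the approximately 276 participants the endpoint is about, so the estimate cannot be computed as written. This rests only on the plan's own definitions; the figure of 276 also depends on its assumption that 20% are detectable at baseline. The practical consequence is limited: a single secondary estimate outside the H1/H2 sequence, with no effect on alpha, power or sample size. It should be corrected before unblinding, so that the population for a prespecified secondary estimate is documented in advance.

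**What to change.** - In Table 5, change the analysis population in the primary-approach row for the Day 14 endpoint in baseline-detectable participants from mITT-VN to mITT-VP.
- Add mITT-VP to the abbreviations under the table.
- In Section 9.5.1, say that mITT-VP is also used for this secondary endpoint. Without this, the section would still mention mITT-VP only for exploratory analyses.

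The cost is one cell, one footnote entry and one sentence, with no new data and no recalculation. Because the endpoint is non-confirmatory, the opening text of Section 9 allows the correction to be documented in the sSAP before unblinding, so a protocol amendment is not needed for this alone.

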9.6.2 Statistical Methods for Safety Analyses

Safety and tolerability will be assessed by clinical review of all relevant parameters including AEs and laboratory tests.

The analysis of safety results for participants will follow a tiered approach (Table 6). The tiers differ with respect to the analyses that will be performed. Adverse events (specific terms as well as system organ class terms) and events that meet PDLCs in laboratory will be classified as belonging to "Tier 2" or "Tier 3" based on the number of events observed.

Safety parameters or adverse events of special interest that are identified a priori constitute "Tier 1" safety endpoints that will be subject to inferential testing for statistical significance. No a priori clinical events of concern have been identified for this study.

Tier 2 parameters will be assessed via point estimates with 95% confidence intervals provided for differences in the percentage of participants with events (via the unstratified Miettinen and Nurminen method (1985) [Miettinen, O. and Nurminen, M. 1985]).

Because many 95% confidence intervals for Tier 2 events may be provided without adjustment for multiplicity, the confidence intervals should be regarded as a helpful descriptive measure to be used in review, not a formal method for assessing the statistical significance of the between-group differences in adverse events and safety parameters that meet predefined limits of change.

ECIs identified in Section 8.4.7 are considered Tier 2 events, as well as the broad AE categories consisting of the percentage of participants with any AE, a drug-related AE, a serious AE, an AE, which is both drug-related and serious, and discontinuation due to an AE will be considered Tier 2 endpoints. In addition, individual AEs observed in $\geq 1\%$ of participants in any intervention group will be categorized as a Tier 2 event. Events reported less frequently than in 1% of participants would obscure the assessment of the overall safety profile and add little to the interpretation of potentially meaningful differences.

Safety endpoints that are not Tier 2 events are considered Tier 3 events. Only point estimates by treatment group are provided for Tier 3 safety parameters.

Continuous Safety Measures

For continuous measures such as changes from baseline in laboratory parameters, summary statistics for baseline, on-treatment, and change from baseline values will be provided by treatment group in Table format.

Safety Tier	Safety Endpoint	95% CI for Treatment Comparison ^a	Descriptive Statistics		
Tier 2	ECIs	Х	Х		
	Any AE	Х	Х		
	Any Serious AE	Х	Х		
	Any Drug-Related AE	Х	Х		
	Any Serious and Drug-Related AE	Х	Х		
	Discontinuation due to AE	Х	Х		
	Specific AEs, SOCs, or PDLCs (incidence ≥1% of participants in one of the intervention groups)	Х	Х		
Tier 3	Specific AEs, SOCs or PDLCs (incidence <1% of participants in all of the intervention groups)		Х		
	Change from Baseline Results in selected laboratory test results		Х		
AE=adverse ev X=results will	ent; CI=confidence interval; PDLC=predefined limit of c be provided.	hange; SOC=systen	n organ class;		
^a 95% CIs wi	^a 95% CIs will be based on the method of Miettinen and Nurminen [Miettinen, O. and Nurminen, M. 1985].				

Table 6Analysis Strategy for Safety Parameters

